[figure not shown]
Title: Sleep duration and risk for obesity in Mexican American children

Number: NCT03947918

Document date: June 3, 2019

PI: [name] (1 K01 HL129087)

Subject: Study protocol

STUDY OVERVIEW

The Summertime: Kids in Motion study is a 3-week study of Mexican American children in the San Francisco area. This study includes six home visits, with the intention of making this study convenient for participants and increase study completion. The RA will make 2 home visits (Monday, Friday) and 1 phone call (Saturday) in Week 1; 1 visit (Friday) and 1 phone call (Saturday) in Week 2; and 1 phone call (Friday) and a final visit (Saturday) in Week 3. In Week 1, children will continue their normal activities. In Week 2, children will be randomized to follow a short (restricted) sleep or long (healthy) sleep schedule. In Week 3, children will be asked to follow the sleep schedule opposite from Week 2. Behavioral assessments over the three weeks will include sleep duration for (Tuesday night-Friday night), physical activity and sedentary behavior (Wednesday-Friday), and dietary intake (Thursday and Friday). A full description is provided below.

STUDY PROCEDURES AND DATA COLLECTION

Recruitment

Recruitment is critical to the study. Participants will be recruited from the community, such as community organizations, youth summer programs, churches, swat meets, parks, and UCSF clinics. Community organizations may be best to recruit from during the week, whereas parks and churches may be the best during the weekend.

When recruiting from any community organization, it will be important to contact them ahead of time over the phone. When going out into to make the initial contact, always have your SFSU student ID or UCSF badge with you and introduce yourself as a research assistant working [name], a researcher at the Univ. of California, San Francisco. You will then describe the study—a study examining how circadian behaviors such as sleep is related to physical activity and eating patterns—and that you are recruiting families with 8-10-year-old Mexican American/Mexican children. Describe the study protocol in short, and that this is a 3-week study. If the organization contact is willing to allow you to recruit participants from that location, then ask when would be the best time to catch parents so that you can speak with them and provide them with study information to participate.

Once you have established the best time to recruit parents, at either community organizations or parks, etc., return at those times to approach parents and give them background on the study. Let them know that you are a student conducting research with [name] at the University of California, Nutrition Policy Institute. We are conducting a study to understand more about sleep and how it is related to children's health. If parent(s) are interested, provide them with more information about the study – that you are recruiting 8-10 year olds and their mother to participate in a 3-week study. There are a total of 4 home visits and 3 phone calls. On the first visit, mothers will be asked to complete a survey and you will measure the child and mom's height and weight. The rest of the home visits and phone calls will be made to ask children about the foods that they eat. Though out the 3-week period, children will be asked to wear a small monitor. One week they will sleep normal, one week they will sleep less, and one week they will sleep more.

If mother/parent is interested, then proceed with the screener [see Study Screener]. If it is confirmed that the family is eligible, then ask them if they would like to schedule their first visit for the upcoming Monday. If Monday is a bad day, then ask if Sunday or Tuesday would be better. If the parent seems disinterested, if it's ok with them, let them know that they can always think about it and that you can contact them at another time. Try not to let the parent refuse. Once they refuse, they are no longer eligible to participate. Ask them if it would be better to call them at a later date. If they agree, then document their name and number.

In the case that the parent is in a rush and needs to call you, or if they saw the information on the flyer and called the number, you will return their calls. [See Recruitment Phone Script for more information.]

If parent agrees to a home visit, schedule the date and get their contact information. The day before the scheduled meeting, you will want to call the parent to remind them of the visit and to make sure that both mom and child are present for the visit. Also, let them know that you will be doing measuring height and weight so that they may want to dress in light clothing/to avoid heavy clothing.

Week 1

Monday (First home visit)

Consent. Upon arriving to their house, introduce yourself as a research assistant(s) working with [name] at the University of California, Nutrition Policy Institute. Wait until the parent invites you in and once you are situated, you can proceed with the participant consent. During this process, you will hand the mother a consent form and let her know what information the document contains. Ask her whether she would like to have it read to her or whether she prefers to read it on her own. If she rather read it on her own, then you can use this time set up the research equipment (scale, stadiometer and computer). Once she has read the form, review the form and the study details with both mother and child. Note that they will be given an incentive for their time and participation. Ask if there are any questions. Once their questions are answered, both mother and child will sign the document. You will also provide them with a copy of the consent form. Make sure to keep the signed form.

After consent. The RA will administer the online Qualtrics survey to the mother using the laptop computer. Individual interviews will last approximately 90 minutes, and will be conducted in the participant's preferred language (Spanish/English). Ask whether the mother prefers to complete the survey on her own on the computer or if she would like you to administer the survey. You can also allow the mother to review the questions on her own if she prefers. Remind her that you will be there to assist her with any questions during this process. If they ask questions about which is the best answer, let them know there is no right or wrong answer. Choose the best answer that is true for her and the child being studied.

After completing the survey, you will then explain that you'll be measuring height, weight and waist for mother and child. If the mother wishes to answer the survey on their own, you can use this time to measure the child. Either way, you will start by measuring the child first and then go on to the mother. [See Anthropometry Protocol.] Then, the RA will provide the accelerometer to the child, and will verbally explain and demonstrate how to wear the monitor to both mother and child [see Activity Monitor Protocol]; written directions will be left with the mother and child [Activity Monitor Instructions]. The child will be asked to wear the monitor for 4 consecutive days

each week (starting on Tuesday and ending on Saturday at noon), except when bathing or swimming. On Wednesday - Friday, children and mothers will be asked to complete a sleep and food diary for the child and to document times that the accelerometer is removed. Mother and child will be given a food reference guide (with illustrations of serving sizes of different foods) to assist them when completing the diary. A pen and accelerometer will be provided in a small box, and the diary, food guide, and accelerometer directions in a folder. Let them know that you will be contacting them through the week to remind them to wear the accelerometer and fill out diaries. Ask whether they prefer texts or phone calls and confirm the best number to be reached at. Lastly, ask them the best time to stop by on Friday for the next visit.

Texts and phone calls. Wednesday through Friday, mothers (and children if applicable) will receive two daily text messages (morning and evening) to remind children to wear the accelerometers and to complete the diaries.

Friday (Second home visit)

Upon arriving, greet the family and wait to be invited in. Make sure that the child has all the items such as the diary and food guide. First, you will have him/her remove the accelerometer and you will download the accelerometer data. Check to see that the child was compliant and that the accelerometer has 50% charge left. If child is missing one day, then ask him/her to keep the accelerometer until Sunday at noon. If they did not comply the whole week then ask them to repeat the week. If they do not want to repeat the week, then ask if they can re-wear it the following week. If they decide to withdraw, then thank them for their time as their participation is voluntary. Let them know that if they change their mind, they should call the number on the consent form.

After downloading data, each participant will be visited to complete a 24-hour dietary recall about Thursday, which will be conducted for Thursday using the Nutrition Data System for Research (NDS-R; Nutrition Coordinating Center, University of Minnesota, Minneapolis, MN). The child will be asked to use their diary and food guide to help facilitate the recall; the RA will go through the diary and recall with the child. [See 24-hr Diet Recall Protocol]. During this visit, you will have the opportunity to show the child how to use the food guide. Also, you will help mothers select a bedtime and wakeup time for the following weeks. Write this down on the front page of the *Sleep and Food Diary*, and on the *Telephone/Texting Contact Form*. At the end of the visit, families will be given a \$25 gift card in appreciation of their time and participation. Before leaving, ask when would be a good time to call on Saturday.

Saturday (Phone call)

The RA will call the child on Saturday to complete a 24-hour dietary recall about Friday. Follow the same protocol as on Friday. After this you can remind the child that he/she is free to remove the accelerometer until Tuesday (unless they are being asked to re-wear), and that you will be making a reminder phone call on Tuesday.

Week 2

Children will be randomized into one of two sleep conditions: long (healthy) sleep or short (restricted) sleep. Participants have already been pre-assigned an ID number and random assignment has been predetermined in order to have an equal number of boys and girls in each condition. [See Participant Randomized Sleep Schedule.] On Tuesday mid-morning, mothers

will be called to notify them regarding which sleep schedule their child will follow in Week 2. You will remind parents of the set bedtime and waking time for both conditions to make sure that their child complies with the sleep schedule. This information should be written on the front page of the *Sleep and Food Diary*, and on the *Telephone/Texting Contact Form*. Children will follow the sleep schedule from Tuesday to Friday night (ending on Saturday).

For the long sleep condition, children will be asked to sleep ≥ 10.5 hrs.

For the short sleep condition, children will be asked to sleep < 8 hrs. If parents are concerned regarding this sleep schedule, you should acknowledge their concern. Remind them that this was discussed in the study consent form, and that you will be monitoring their child for daytime drowsiness, which is a possible side effect. It is ok for their child to nap. Also, reassure them that you will be monitoring their child and calling them to make sure that they are not experiencing too much daytime drowsiness.

Child-mother pairs will continue to receive 2 daily texts or phone calls (Wednesday-Friday) as a reminder to wear the accelerometer, to complete sleep and food diaries, and to remind them of their bedtime and wake up time (as discussed).

Children in the Short Sleep Condition will be called and asked to complete the Pediatric Daytime Drowsiness Scale (Thursday). You will calculate their drowsiness score and discuss with [name] if the score is 13 or higher. The parent will also be advised. Encourage their child to take naps and that this part of the study is almost complete. If they wish to withdraw from the study, then that is ok, as their participation is voluntary.

Friday (Third home visit)

Children will be visited on Friday. Make sure that the child has the diary and food guide. Have him/her remove the accelerometer and download the accelerometer data. Check for compliance and accelerometer charge. If child is missing one day, then ask him/her to keep the accelerometer on until Sunday at noon. If they did not comply the whole week then ask them to repeat the week. If they do not want to re-wear and decide to withdraw, then thank them for their time.

After checking accelerometer compliance, you will perform a 24-hour dietary recall about Thursday. Once again, you will use the diary and the food guide. Upon completion of the visit, the family will be given a \$25 gift card for their time and participation in Week 2. Before leaving, ask when would be a good time to call on Saturday.

Saturday (Phone call)

Child participant will receive a phone call on Saturday and asked to complete a 24-hour dietary recall about Friday. Follow the same protocol as on Friday, using the diary and food guide. After this you can remind the child that he/she is free to remove the accelerometer until Tuesday (unless they are being asked to re-wear), and that you will be making a phone call on Tuesday as a reminder.

A 3-night period between sleep conditions will follow.

Week 3

During Week 3, participants will cross over to the opposite sleep condition. Each child will follow the opposite sleep schedule from Week 2. This means that if they were in the short sleep condition in Week 2, then they will follow the long sleep condition in Week 3. You will remind mothers about bedtime and wakeup time to make sure that their child complies with the sleep schedule. This information should be written on the front page of the *Sleep and Food Diary*, and on the *Telephone/Texting Contact Form*. On Tuesday mid-morning, mothers will be called to notify them about which sleep schedule their child will follow in Week 3.

Child-mother pairs will continue to receive 2 daily texts or phone calls (Wednesday-Friday) as a reminder to wear the accelerometer, to complete sleep and food diaries, and to remind them of their bedtime and wake up time (as discussed).

Short Sleep Condition: You will call children in the short sleep condition to administer the Daytime Drowsiness Scale. Calculate their score, and follow the same procedure as Week 2. Follow same protocol as in Week 2. Remind the mother that this is the last week of the study and that their participation is almost complete. If the parent asks to withdraw from the study, then that is ok, as their participation is voluntary.

Friday (Phone call)

On Friday, children will receive a phone call and will be asked to complete a 24-hr dietary recall for Thursday. Follow procedures as in prior the weeks using diary and food guide.

Saturday (Last home visit)

The last visit will occur on Saturday, at which time the accelerometer data will be uploaded and the child will complete a final 24-hr dietary recall for Friday. All families will complete an exit interview to discuss challenges and positive aspects to participating in the study, ideas to facilitate participation, and barriers to and facilitators of longer sleep duration. [See Exit Survey.] Upon completion, families will receive a \$40 gift card.

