Title: Sleep duration and risk for obesity in Mexican American children

Number: NCT03947918

Document date: June 16, 2020

PI: [name] (1 K01 HL129087)

Subject: Analysis plan

Analysis includes using 2-way repeated measures ANOVA. First, I will test for order effects (8 hr condition assigned first versus second) including the order main effect and the sleep-condition-by-order interaction. Non-significant order effects will be dropped and the model refit, as appropriate. If some order effects are retained in the model, then I will perform custom contrasts within each order condition, e.g., 8 v. 10.5 hrs within each order condition; and across order conditions, e.g., 8 hrs in the 8-hr-first condition versus 8 hrs in the 10.5-hr-first condition. These models will mostly focus on differences between sleep conditions.

I can use the usual sleep condition to categorize children in terms of the regular sleep duration, which can be used as either as a continuous or a categorical (e.g.,  $\leq 9$  v.  $> 9$  hrs) covariate in the regression models. This would allow testing the interaction between usual sleep duration (whether categorical or continuous) and assigned sleep duration (8 v. 10.5 hrs). If order effects are operating, i.e., significant condition-by-order interaction, then I will test 3-way interactions: condition-by-order-by-X, where X is a variable derived from the regular sleep condition, i.e., either continuous covariate or binary.

I will average Thursday and Friday dietary intake (e.g., caloric intake) and PA within week 2 and week 3, using week 1 dietary intake and PA as covariates. I will also test all 4 assessments of dietary intake and PA (Thursday and Wednesday for week 2 and week 3) in a single repeated measures model, using week 1 assessments (Thursday and Friday) as covariates. Time can be treated as a continuous or categorical variable (week 2-Wed.; week 2-Thurs; week 3-Wed.; week 3-Thurs). If categorical, I can then compare dietary intake and PA within each day of the week (e.g., Wed. and Thurs.) within each assigned sleep condition.

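### Sleep order is tied to pre-assigned IDs before Week 1 losses have occurred, so the intended sex balance per order can be lost, and no step for concealing the schedule is described

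*Protocol*

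**What the plan says.** The protocol is written as a manual addressed to the research assistant. Under Week 2 it states that "Participants have already been pre-assigned an ID number and random assignment has been predetermined". The purpose it gives is balance by sex, namely "in order to have an equal number of boys and girls in each condition". It then points the reader to a separate attachment: "See Participant Randomized Sleep Schedule". On Tuesday of Week 2 mothers "will be called to notify them regarding which sleep schedule their child will follow in Week 2". Under Week 3, "During Week 3, participants will cross over to the opposite sleep condition", so the Week 2 condition fixes the order.

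The same manual covers recruitment and screening ("If mother/parent is interested, then proceed with the screener [see Study Screener"), consent at the first home visit, and the Week 1 data. At the Week 1 Friday visit a non-compliant family is offered longer wear, a repeat of the week or re-wear the week after. The text then adds: "If they decide to withdraw, then thank them for their time as their participation is voluntary".

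The SAP's first paragraph tests the order main effect and the condition-by-order interaction, and then says: "Non-significant order effects will be dropped and the model refit, as appropriate".

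The documents do not say when an ID is linked to a child, who made or holds the schedule, when the assistant may open it, or what happens to the ID of a child who leaves in Week 1.

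**The concern.** Two things follow from fixing the order to the ID in advance.

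First, balance on a list is not balance among the children who start Week 2. Week 1 is a usual-activity week in which nobody is yet on a sleep schedule. A child lost in that week uses up a place in one sex-by-order cell, and no replacement rule is given.

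Second, the manual's reader recruits families, takes consent, runs the Week 1 dietary recall and helps mothers choose bed and wake times. The SAP uses Week 1 intake and activity as covariates. If that person knew the order in advance, these steps could be influenced, even unintentionally. Nothing in the text rules this out.

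The statistical stake is the period effect. In a two-period crossover the condition-by-order interaction is the period effect. With equal orders it cancels from the average within-child difference. With unequal orders it does not, and the SAP's rule of dropping non-significant terms removes the adjustment.

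**Working it through.** The plan gives no sample size, block size, loss rate or period effect, so there is no figure to reproduce. Everything numerical below is illustrative.

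**1. How the period effect enters.** Let τ be the short-minus-long effect and π the Week 3 minus Week 2 effect. A child given long sleep first has expected difference τ + π; a child given short sleep first has τ − π. With n1 and n2 children in these two orders and the interaction dropped, the pooled mean difference is

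τ + π × (n1 − n2)/(n1 + n2).

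**2. Is exact balance likely to survive Week 1?** Assume N/4 children in each sex-by-order cell, independent loss at rate d and no replacement. The chance that both sexes stay balanced is [Σ Binom(k; N/4, 1−d)²]².

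| N | d = 5% | 10% | 20% | 30% |
|---|---|---|---|---|
| 20 | 41% | 21% | 10% | 7% |
| 40 | 21% | 10% | 5% | 4% |
| 60 | 14% | 6% | 3% | 2.5% |
| 80 | 10% | 5% | 2.5% | 2% |

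Exact balance would usually be lost, but the imbalance is small: the median difference between orders is 1 to 3 children.

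**3. Size of the share.** With N/2 children per order and the same loss model, the exact distribution of |n1−n2|/(n1+n2) gives these medians (95th percentile in brackets):

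| N | d = 5% | 10% | 20% | 30% |
|---|---|---|---|---|
| 20 | 5% (11%) | 5% (18%) | 7% (25%) | 9% (33%) |
| 40 | 3% (8%) | 3% (11%) | 6% (16%) | 7% (21%) |
| 60 | 2% (5%) | 3% (9%) | 4% (13%) | 5% (17%) |
| 80 | 1% (5%) | 3% (7%) | 3% (11%) | 5% (15%) |

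A rough check: the share has standard deviation of about √[d/(N(1−d))]. For N = 20 and d = 30% this is √(0.3/14) = 0.146, and 0.674 × 0.146 = 9.9%, close to the exact 9%.

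**4. A tail case.** A 16:12 split gives (16−12)/28 = 14.3%. To reach it from 16:16 with four losses, all four must fall in one order: 2 × C(16,4)/C(32,4) = 2 × 1,820/35,960 = 10.1%. More extreme splits are rarer. Reaching 17:11 from 17:17 with six losses has chance 2 × 12,376/1,344,904 = 1.8%, for a share of 6/28 = 21.4%.

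**5. Does the SAP's test protect the estimate?** Take 16:12 and assume π = 0.25 SD of the within-child difference. The two orders then differ by 2π = 0.5 SD, so the noncentrality is 0.5/√(1/16 + 1/12) = 1.31. A two-sided 5% test on 26 degrees of freedom is non-significant about 76% of the time. The term is then dropped and the 14.3% share remains. The resulting bias is 0.143 × 0.25 = 0.036 SD, against a standard error of 1/√28 = 0.189 SD, or about 0.19 standard errors.

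**6. Cost of keeping the term.** The variance ratio relative to balanced orders is (1/n1 + 1/n2)/(4/(n1+n2)). At 16:12 it is 0.1458/0.1429 = 1.02. Over the grid above the mean inflation is 0.1% to 2.7%, and the 95th percentile is at most 12.5% (N = 20, d = 30%).

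**The case against.** A reader might infer that the assistant knows each child's order before enrolment. The documents do not say so. The schedule is cited under Week 2, just before the Tuesday call, which is when it is needed. It is a separate attachment, and a list generated in advance is ordinary practice if it is concealed. What the text supports is that concealment is not described.

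A reader might also infer that withdrawals necessarily break the balance. Withdrawal is only allowed for, after other options have been offered, and losses may fall evenly. Because mothers learn the order only on the Week 2 Tuesday, no stated mechanism makes Week 1 loss depend on order.

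Three further points stand. Every child who completes both weeks receives both conditions, so steering children into one order would mainly distort comparisons between orders, not the within-child contrast. The SAP's second model, with all four assessments and a time variable, can carry the period effect directly. And withdrawal is also permitted in Weeks 2 and 3, so later assignment cannot by itself guarantee balance among the children analysed.

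These arguments limit the size of the point but do not remove it. The averaged analysis has no such time term once the interaction is dropped, and nothing in the SAP would correct selective entry if it occurred.

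**Conclusion.** The point holds as a small, inexpensive improvement. The stated method does not protect the sex-by-order balance it aims for, and the plan does not show that the schedule is concealed until Week 1 is over.

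Under assumed sizes of 20 to 80 children and losses unrelated to order, the median share of the period effect entering the sleep contrast is about 3% to 9% at 10% to 30% loss, and 1% to 5% at 5% loss. Over the whole grid the 95th percentile runs from 5% to 33%. The share matters only if a period effect exists and the condition-by-order term is dropped. Shares of 14% or more lie in the upper part of these distributions and should not be read as typical. The documents support no finding that enrolment was in fact steered.

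**What to change.** - Assign the order only after a child has completed Week 1, from separate boy and girl lists in small blocks.
- Have the investigator hold the lists and release each order on the day of the Week 2 Tuesday call. Keep the study ID separate from the order.
- In the SAP, keep the period (condition-by-order) term in the model regardless of significance, because withdrawals in Weeks 2 and 3 can still unbalance the orders.
- If allocation has already taken place, report who held the schedule, when it could be seen, how IDs of Week 1 withdrawals were handled, and the numbers by sex and order starting Week 2. The analysis change can still be made.

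The cost is one message per child before a call that is already planned, and one degree of freedom in the model. Families learn the order at the same time as now.

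### Allocation is balanced by sex but no SAP model includes sex, so the order main effect and the across-order contrasts have standard errors slightly too large; the sleep-condition comparison is not affected

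*Protocol*

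**What the plan says.** **Allocation.** The protocol, under Week 2, states that "random assignment has been predetermined in order to have an equal number of boys and girls in each condition". Under Week 3 it adds that "Each child will follow the opposite sleep schedule from Week 2". Every child therefore receives both conditions, and what is randomised is the order. Balance by sex in each Week 2 condition is balance by sex in each order.

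**Order test.** The SAP's first paragraph tests for order effects "including the order main effect and the sleep-condition-by-order interaction". Terms that are not significant are removed and the model is refitted.

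**Contrasts if order effects are kept.** These are of two kinds: "8 v. 10.5 hrs within each order condition", and across orders, for example "8 hrs in the 8-hr-first condition versus 8 hrs in the 10.5-hr-first condition".

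**Main target.** "These models will mostly focus on differences between sleep conditions".

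**Covariates.** The SAP's third paragraph averages the outcomes by week, "using week 1 dietary intake and PA as covariates", and also uses week 1 values in the single repeated measures model. Usual sleep duration "can be used as either as a continuous or a categorical" covariate, as an option.

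**Sex.** It is not named as a term in any model. The nearest mention is the check for demographic differences between missing-data patterns in the SAP's last paragraph, which is not an outcome model.

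**The concern.** A factor used to balance the allocation normally belongs in the analysis. Balancing removes sex from the sampling variation of a comparison between orders. If the model omits sex, the boy-girl difference stays in the residual, and the model reports more uncertainty than the design leaves. The estimate is sound, its SE is too large, and the test rejects less often than its nominal level.

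This matters only where different children are compared. In this plan those comparisons are the order main effect and the across-order contrasts. The first acts as a gate: a term that fails the test is removed. A conservative test would discard a real order difference a little more often than intended.

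**Working it through.** **Which planned comparisons contain sex.** Write a child's outcome as a sex term (constant over weeks) plus condition, period and residual terms.

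- *Order main effect:* compares child means between the two orders. Different children, so sex variance is in the error term.
- *Same condition across orders:* compares one week's value between orders. Different children, so sex variance is in the error term.
- *Condition-by-order interaction:* compares each child's short-minus-long difference between orders. That difference is week 2 minus week 3 in one order and week 3 minus week 2 in the other, so the interaction is the period effect. The sex term cancels within each child.
- *Within-order contrasts and the overall condition contrast (complete data):* within-child differences. The sex term cancels.

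**Inputs.** The documents give no sample size, SD, alpha, effect size or sex difference, so there is no figure to reproduce. Assumed: within-sex SD 1; half boys and half girls, balanced by order; sex gap d = 0.3, 0.5 or 0.8 SD of the quantity compared; two-sided alpha 0.05; correlation ρ of week 1 with the later value 0.3 to 0.7; same sex gap in week 1.

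**Formulas.** With s = d²/4 (the variance due to sex), omitting sex multiplies the model SE by:

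- without a week 1 covariate: r = √(1 + s)
- with it: r = √{[(1 + s) − (ρ + s)²/(1 + s)] / (1 − ρ²)}

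The type I error is 2[1 − Φ(1.960 r)]. For an effect with 80% power when sex is fitted, power falls to Φ(1.960 + 0.842 − 1.960 r).

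Worked case, d = 0.5, ρ = 0.5: s = 0.0625. Without the covariate, r = √1.0625 = 1.031. With it, r = √[(1.0625 − 0.5625²/1.0625)/0.75] = √(0.7647/0.75) = 1.010.

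| d | SE inflation, no covariate | ρ = 0.3 | ρ = 0.5 | ρ = 0.7 |
|---|---|---|---|---|
| 0.3 | 1.1% | 0.6% | 0.4% | 0.2% |
| 0.5 | 3.1% | 1.6% | 1.0% | 0.5% |
| 0.8 | 7.7% | 3.6% | 2.3% | 1.2% |

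Without the covariate, type I error is 4.75%, 4.3% and 3.5%, and power is 79.4%, 78.3% and 75.5%. With the covariate at ρ = 0.5, type I error is 4.9%, 4.8% and 4.5%.

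**Scale of d.** The order main effect uses a child's mean of two weeks, which has a smaller SD. If d is instead in single-week SDs and all weeks correlate at 0.5, the within-sex variance of that mean is (1 + 0.5)/2 = 0.75. At d = 0.5 the inflation is then √(1 + 0.0625/0.75) = 1.041 without the covariate. With it, the inflation is √[(0.8125 − 0.5625²/1.0625)/(0.75 − 0.25)] = √(0.5147/0.5) = 1.015. This is somewhat larger, but of the same order.

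**Simulation.** 20,000 two-period crossover trials; 20 children per order (assumed); d = 0.5 in single-week SDs; week 2 to week 3 correlation 0.5; no week 1 covariate.

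| Comparison | True SD | Model SE, sex omitted | Model SE, sex included | Type I omitted / included |
|---|---|---|---|---|
| Order main effect | 0.274 | 0.283 | 0.272 | 4.2% / 5.0% |
| 8 h across orders | 0.316 | 0.324 | 0.314 | 4.5% / 5.1% |
| Condition by order | 0.316 | 0.314 | 0.314 | 4.9% / 4.9% |

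Fitting sex restores the nominal error rate for the two between-child tests and leaves the interaction unchanged.

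**The case against.** The case for leaving the plan alone is strong on size. The models are aimed at the sleep-condition difference, which is within child. The across-order contrasts are run only if an order effect is retained. The week 1 covariates already absorb much of any stable boy-girl difference. What remains is a slightly conservative screening test and no bias. All of this stands, and it is why the point is minor. It does not remove the omission, because the covariates leave a remainder and the factor is already known. The SAP also does not say outright that the order test in its first paragraph is run with the week 1 covariates, so both sets of figures are relevant.

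Three stronger readings are tempting, but the documents do not support them.

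- A reader might infer that the whole order test is between children. It is not: one of its two terms, the interaction, is the within-child period effect. That is also the term that triggers the three-way tests.
- A reader might infer that the sleep-condition result is biased or less precise. With complete data, a constant sex difference cancels from it.
- A reader might infer that children with only one week of data bring sex variance into the condition estimate through the likelihood method. The SAP specifies repeated measures ANOVA for condition and order, and its last paragraph ties full likelihood to pathways to weight status. It does not clearly say the condition models are fitted that way, so this is only an inference.

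**Conclusion.** The point holds in a narrow form: the order main effect and the across-order contrasts omit the factor that balanced the allocation, so they are slightly conservative. With the gap measured in SDs of the quantity compared, SE inflation is about 1% to 8% without the week 1 covariate and about 0.2% to 4% with it. Those ranges rest on assumed sex gaps of 0.3 to 0.8 SD, assumed correlations of 0.3 to 0.7, and a sex difference that is constant over weeks. None of these comes from the documents. No planned conclusion about short versus long sleep is shown to be wrong.

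**What to change.** Add one sentence to the SAP prespecifying sex as a fixed factor in the repeated measures models for condition and order, because it is the factor used to balance the allocation. If a likelihood model is used so that children with one week of data contribute, include sex there too, and state in the SAP which models are fitted that way. The cost is the wording and one between-child degree of freedom. The design does not change, and the complete-data condition contrast keeps its value.
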